Patients will be identified in the National Prescription Database. They will be linked to the National Death Indices, National Cancer Registries and National Hospital Discharge schemes to identify cases of cancer, pancreatitis and anyone who has died. Clinical data for all patients with the outcome of interest will also be retrieved from National Hospital Discharge schemes. Additional data will be collected from other (country specific) available data sources.

The personal identification number will be used to link unambigously the databases in each country. The ATC coding system (Anatomic Therapeutic Coding) will be used to identify exposure: all patients having been prescribed drugs for the treatment of diabetes (ATC code A10 and subcategories) will be retrieved and linked to the other databases: they will be followed via cancer and hospital discharge registries. The ICD10 codes will be used for outcome assessment: acute pancreatitis (K85), pancreatic cancer (C25) and thyroid cancer (C73), especially medullary thyroid cancer.

III.9.5 Study Size

All available data following the launch of lixisenatide will be analyzed for the final analyses. The data from the three participating countries will be combined together for the analysis. The estimation of sample size and study power for the objectives of this study will be further defined after consultation with local Principal Investigators and external experts.

According to estimates provided by the International Diabetes Federation for 2013, there were 1,049,810 prevalent cases of diabetes among adults aged 20-79 in the three countries combined (346,730 in Denmark; 209,870 in Norway; and 493,210 in Sweden). In addition, assuming a crude incidence rate of diabetes of 364 per 100,000 personyears (calculated using data for 1995-2006, from Carstensen et al, 2008), then for a total adult population of 15,000,000 persons, approximately 55,000 new cases of diabetes will be diagnosed every year in the three countries combined. This provides an estimate of the numbers of new cases of diabetes that are potentially eligible for the study. Not all of these patients will be candidates for treatment with lixisenatide for a variety of reasons. However, various scenarios about the prevalence of patients prescribed lixisenatide are made in order to estimate the statistical power of the Registry study. These estimates are presented in Table III.9.5.1 and Table III.9.5.2.

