Using these hypothetical numbers, the number of patient-years accumulated over a period of 5 years of registry were calculated as follows:

1st year of registry: no records yr1 = %lixi * prevalence diabetes = %lixi * 1,049,810 2nd year of registry: no records yr2 = no records yr1 + new records yr2= no_records_yr1 + %lixi * new_cases_diabetes = no_records_yr1 + %lixi * 55,000 3rd year of registry: no_records_yr3 = no_records_yr2 + new_records_yr3 = no_records_yr1 + 2 * %lixi * new_cases_diabetes

etc...

Thus the number of person-years accumulated over 5 years is: Person-years_over_5_years = no_records_yr1 + no_records_yr2+..+ no_records_yr5 =5*(%lixi*prevalence_diabetes)+10*(%lixi*new_cases_diabetes)

The number of expected cases of pancreatitis were calculated using the incidence rate shown above (65.57 per 100,000 person-years). The power of the study was then calculated for the expected number of cases as a mean of Poisson law (Breslow and Day, 1987) and a range of expected vs observed ratios. The results are shown in Table III.9.5.1.

Table III.9.5.1: Estimates of statistical power for Registry Study for pancreatitis under different scenarios for prevalence of prescription of lixisenatide.

Pancreatitis (incidence rate=65.57/100,000 pyrs)						
	Pyrs No of Power in order Power in order Power in o					
% exposure to	accumulated	expected	to detect	to detect	to detect	
lixisenatide	over 5 years	cases	obs/exp+=1.2	obs/exp+=1.5	obs/exp+=2	
0.10%	5799.05	3.8	0.10*	0.17	0.39	
0.20%	11598.1	7.6	0.13*	0.26	0.64	
0.50%	28995.25	19.0	0.18	0.60	0.97	
0.80%	46392.4	30.4	0.27	0.79	1.00	
1.00%	57990.5	38.0	0.29	0.83	1.00	
1.50%	86985.75	57.0	0.37	0.93	1.00	
2%	115981	76.0	0.47	0.98	1.00	
5%	289952.5	190.1	0.38*	1.00	1.00	
10%	579905	380.2	0.60*	1.00	1.00	
*Calculated using normal approximation						
tobs /exp stands for 'observed us expected ratio'						

+obs/exp stands for 'observed vs expected ratio

These numbers are certainly underestimated, as the incidence of diabetes has been steadily increasing worldwide. Even so, for a 1% exposure to lixisenatide among diabetic patients, thus 38 expected cases of pancreatitis, the power of the study in order to

detect an observed vs expected ratio of pancreatitis of 1.5 will be of 83% (significance level=0.05).

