Table III.9.5.2 shows the power calculation for the Patient Registry Study and cancer (pancreatic cancer and thyroid cancer). For 1% of exposure to lixisenatide among the diabetic population the study will be able to detect an observed vs expected ratio of pancreatic cancer of 1.5 with 59% power (significance level=0.05), and an observed vs expected ratio of 2 with 92% power (significance level=0.05). For 1% exposure to lixisenatide, the study is underpowered to detect these same ratios of thyroid cancer, it will be able to detect with power of 92% an observed vs expected ratio of 2 (significance level=0.05) for 5% exposure to lixisenatide among the diabetic population.

Table III.9.5.2 : Estimates of statistical power for Registry Study for pancreas cancer and thyroid cancer under different scenarios for prevalence of prescription of lixisenatide.

Pancreatic cancer (incidence rate=29.19/100,000 pyrs)				
	Pyrs	No of	Power in order	Power in order to
% exposure to	accumulated	expected	to detect	detect
lixisenatide	over 5 years	cases	obs/exp+=1.5	obs/exp+=2
0.10%	5799.05	1.7	0.07	0.14
0.20%	11598.1	3.4	0.17	0.39
0.50%	28995.25	8.5	0.32	0.73
0.80%	46392.4	13.5	0.48	0.90
1.00%	57990.5	16.9	0.59	0.92
1.50%	86985.75	25.4	0.74	>0.98
2%	115981	33.9	0.79	1.00
5%	289952.5	84.6	0.99	1.00
10%	579905	169.3	1.00	1.00
	Thyroid cancer (incidence rate	=6.13/100,000 py	rs)
	Pyrs	No of	Power in order	Power in order to
% exposure to	accumulated	expected	to detect	detect
lixisenatide	over 5 years	cases	obs/exp+=1.5	obs/exp+=2
0.10%	5799.05	0.4	<0.07	<0.14
0.20%	11598.1	0.7	<0.07	<0.14
0.50%	28995.25	1.8	0.07	0.14
0.80%	46392.4	2.8	0.08	0.21
1.00%	57990.5	3.6	0.17	0.39
1.50%	86985.75	5.3	0.22	0.54
2%	115981	7.1	0.26	0.64
5%	289952.5	17.8	0.59	0.92
10%	579905	35.5	0.83	1.00
+obs/ovp stands	for 'obsorved us	whether a the		

+obs/exp stands for 'observed vs expected ratio'

Thus, a prevalence of 0.08% of patients with diabetes prescribed lixisenatide would give the study an 80% power to detect a risk of 1.5. Similar calculations reveal that for pancreas cancer the corresponding prevalence of lixisenatide prescription to give 80% power would be 2% and for thyroid cancer 9%.

III.9.6 Data Management

Once the study population well defined via prescription registries, it will be essential to collect the follow-up data efficiently.

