² An external blinded committee (Pancreatic Safety Assessment Committee or PSAC) has been appointed to review all pancreatic adverse events occurring in clinical trials of lixisenatide. The PSAC Charter has not been finalized, yet. However, the criteria for adjudication of acute pancreatitis will be adapted from those proposed by Banks, Freeman, and the Practice Parameters Committee of the American College of Gastroenterology (Am J. of Gastroenterology 2006;101:2379-2400) and Frossard et al. (Lancet 2008;371:143-52.).

Similarly to the Database Study, each national centre will be responsible for the data storage and data management of the individual-level data, following all national and European directives regarding the well being and rights of each study subject. Each centre has an excellent track record of successfully undertaking similar research respecting all moral and legal requirements.

Only de-identified data will be stored at IPRI, and this will be done in a secure manner: data will password protected, and stored on local machines.

III.9.7 Data Analysis

Descriptive analysis will be performed and total follow-up time for lixisenatide users will be calculated.

Figure II.9.7.3: General study overview

For acute pancreatitis, pancreatic cancer and thyroid cancer, the expected number of cases will be estimated annually after launch using the background rates obtained from the retrospective databases study.

If the observed number of cases for the events of interest, respectively, is significantly higher than the expected number of cases, further investigation may be warranted following discussion with the regulatory authorities.

An independent **Scientific Steering Committee** will be appointed to oversee the study and advise on treatment, methodological and biostatistical issues. This group will meet regularly throughout the duration of the study and incorporate a **Biostatistical Advisory Group**, to advise on all aspects of the design and data analysis.

The Scientific Steering Committee will comprise:

[name] University of Perugia Perugia, Italy

[name] University College London London, United Kingdom

[name] Robertson centre for Biostatistics University of Glasgow, Glasgow, United Kingdom

[name] Department of Biostatistics Yale University School of Public Health New Haven, United States of America

[name] McMaster University, Hamilton, Canada

[name] Mount Sinai Hospital New York, United States of America.

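### Registry power (III.9.5): the exposure said to give 80% power for pancreatitis is about ten times too low, and two cells of Table III.9.5.1 are wrong

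*Protocol*

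**What the plan says.** Section III.9.5 (Study Size) builds the Registry power from three inputs. For the diabetic population it says that "there were 1,049,810 prevalent cases of diabetes among adults aged 20-79 in the three countries combined" and that "approximately 55,000 new cases of diabetes will be diagnosed every year in the three countries combined". For the event rate the table header reads "Pancreatitis (incidence rate=65.57/100,000 pyrs"). For the method: "The power of the study was then calculated for the expected number of cases as a mean of Poisson law", applied to a range of observed-to-expected ratios.

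Table III.9.5.1 gives power 0.17 for a pancreatitis ratio of 1.5 at 0.10% exposure (3.8 expected cases) and 0.79 at 0.80% (30.4 expected cases). In the ratio 1.2 column, power is 0.47 at 2% exposure (76.0 expected cases), 0.38 at 5% (190.1) and 0.60 at 10% (380.2). The last two cells carry a star, explained as "Calculated using normal approximation".

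After Table III.9.5.2 the section concludes that "a prevalence of 0.08% of patients with diabetes prescribed lixisenatide would give the study an 80% power to detect a risk of 1.5". The sentence names no outcome. The next one gives the corresponding exposures as 2% for pancreatic cancer and 9% for thyroid cancer, so this one must concern pancreatitis.

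The significance level is given as 0.05, without saying whether the test is one- or two-sided. Section III.9.7 sets the trigger: if the observed count "is significantly higher than the expected number of cases, further investigation may be warranted".

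**The concern.** The closing sentence and the table cannot both be right. The table already puts power at 0.17 for an exposure slightly above 0.08%, and reaches about 0.8 only at ten times that exposure. The ratio 1.2 column is also implausible on its face: expected cases rise 2.5-fold from 76.0 to 190.1 while the stated power falls from 0.47 to 0.38.

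The sentence is worded as the conclusion of the power section. Read literally, it says that about three expected cases suffice, so a null result at that uptake could be taken as reassuring when the chance of detecting a 50% excess is under one in five. The two cells err the other way: they suggest that even 5% to 10% uptake would be weak for detecting a 20% excess.

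**Working it through.** **Inputs** (all III.9.5): 1,049,810 prevalent cases; 55,000 new cases a year; 65.57 per 100,000 person-years; significance level 0.05. Sidedness is not stated, so both versions are shown.

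**Person-years and expected cases.** With exposure p, person-years over five years = 5 × p × 1,049,810 + 10 × p × 55,000 = p × 5,799,050. Expected cases E = person-years × 65.57/100,000. At 1%: 57,990.5 person-years and E = 38.0, as printed. All pancreatitis rows reproduce in the same way.

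**Power.** Take the smallest c with P(X ≥ c | E) ≤ α. Power for ratio R is then P(X ≥ c | R × E), with α = 0.05 (one-sided) or 0.025 in the upper tail (two-sided).

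**The 0.08% sentence.** Person-years = 0.0008 × 5,799,050 = 4,639, so E = 3.04.
- One-sided: c = 7, P(Poisson(4.56) ≥ 7) = 0.177.
- Two-sided: 0.09.

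Neither is near 0.80. At 0.80% exposure (E = 30.4) exact one-sided power is 0.77, against 0.79 printed. The companion figures point the same way: 2% for pancreatic cancer is 0.02 × 5,799,050 × 29.19/100,000 = 33.9 expected cases, and 9% for thyroid cancer is 0.09 × 5,799,050 × 6.13/100,000 = 32.0. An exposure of 0.8% belongs with these (30.4 cases); 0.08% (3.0 cases) does not.

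**Where 80% is reached.** Exact one-sided power for ratio 1.5 moves in a saw-tooth: on a grid of 0.005 percentage points it first passes 0.80 at 0.815% exposure, is 0.78 at 0.84%, and stays at or above 0.80 from about 0.87% (E = 33.1). The square-root normal approximation, Φ(2(√(RE) − √E) − 1.645), gives 0.805%. Two-sided, about 1.0% to 1.1% is needed.

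**The ratio 1.2 cells.**

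| Exposure | E | Printed | Exact one-sided | Square-root approx., one-sided | Exact two-sided |
|---|---|---|---|---|---|
| 2% | 76.0 | 0.47 | 0.48 | 0.51 | 0.36 |
| 5% | 190.1 | 0.38 | 0.83 (c = 214) | 0.84 | 0.74 |
| 10% | 380.2 | 0.60 | 0.98 (c = 414) | 0.98 | 0.96 |

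The square-root approximation does reproduce the two small starred cells (0.10 at 0.10% and 0.13 at 0.20% exposure), so the footnoted method does not explain the large ones. It would return 0.38 and 0.60 at about 49 and 99 expected cases, which suggests that wrong counts were entered; that cause is a guess. Score, Wald and log-scale variants, one- or two-sided, do not give the pair either.

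**Sidedness of the other cells.** At the printed expected counts, exact one-sided power does not match every unstarred cell. For ratio 1.5 at E = 7.6 it is 0.36 against 0.26 printed; at E = 38.0 it is 0.87 against 0.83. Agreement within two points comes at nearby round counts (3, 7, 20, 30, 35, 50, 70). For example, E = 30 gives 0.274 and 0.792 for ratios 1.2 and 1.5 (printed 0.27 and 0.79), and E = 35 gives 0.288 and 0.833 (printed 0.29 and 0.83).

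**The case against.** The best defence is that little turns on these numbers. The 0.08% is evidently a misplaced decimal, and a reader with Table III.9.5.1 open can correct it. All available data will be analysed whatever the uptake, no recruitment target or stopping rule uses the figures, and III.9.5 says that power will be further defined. The two cells understate power, and no sentence in the protocol draws on them. This stands as an argument about severity. It does not make the printed figures right.

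Three stronger readings are tempting, and the documents do not support them.

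- A reader might infer that the Registry's headline power is wrong. It is not affected. The statement that the power to "detect an observed vs expected ratio of pancreatitis of 1.5 will be of 83% (significance level=0.05") rests on the 1% row, as do the synopsis figures for pancreatic cancer; the synopsis thyroid figure rests on the 5% row of Table III.9.5.2. None uses the 0.08% or the ratio 1.2 column, and 83% is slightly conservative against 0.87 exact at E = 38.0.
- A reader might argue that power can never fall as expected cases rise. Exact Poisson power does dip locally: for ratio 1.5 it goes from 0.794 at 0.79% exposure to 0.773 at 0.80%. The cells are wrong because a fall from 0.47 at E = 76 to 0.38 at E = 190 is far larger than such dips, and because direct calculation gives 0.83.
- A reader might conclude that the table fits only a one-sided 5% test. One-sided is the best explanation and suits a trigger that acts only on an excess, but the fit needs rounded counts that the protocol does not mention. At 0.20% exposure and ratio 1.5, the two-sided value at the printed count (0.26) happens to match.

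**Conclusion.** The closing sentence of III.9.5 is wrong by a factor of about ten. At 0.08% exposure, power for a pancreatitis ratio of 1.5 is about 0.18 one-sided (0.09 two-sided), not 0.80. The value that fits the table is about 0.8%. The ratio 1.2 cells at 5% and 10% exposure are wrong under any standard one-sample Poisson test: about 0.83 and 0.98 one-sided, or 0.74 and 0.96 two-sided. The printed values are 46% and 61% of the one-sided ones (52% and 63% of the two-sided).

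These results rest on the protocol's own population, rate and person-years formula, and on treating the expected count as fixed, as the protocol does. One-sided testing at 5% is an inference. Both errors stand without it; only the replacement values depend on it. This is a moderate arithmetic correction that leaves the design and the synopsis power figures unchanged.

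**What to change.** In the closing sentence of III.9.5, replace 0.08% with about 0.8% and name pancreatitis as the outcome. If a guaranteed 80% is wanted on the exact one-sided test, the figure is roughly 0.87%. In Table III.9.5.1, replace 0.38 and 0.60 with about 0.83 and 0.98. If these are entered as exact values, remove the star from those cells. State beside the tables that the test is one-sided at 5%; if two-sided testing is intended, the values become 0.74 and 0.96, and about 1.0% to 1.1% exposure is needed for 80% power.

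Preferably, recompute the whole table at its printed expected counts by one stated method, because patching two cells leaves it on a mixed basis.

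The minimum is three numbers and one sentence. A full recomputation is a short script. Neither changes the design, the data collection or the analysis.

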A new user approach will be favoured in order to reduce prevalent user bias and confounding from covariates that could be associated with drug use (Ray, 2003). New users are defined as patients who initiated **either GLP-1 treatment or other antidiabetic drugs** at least 6 months after the start date of the study (this will include patients who are treatment naive in regards to any anti-diabetic medication although this group will be very few in numbers). The 6 months 'criterion' was defined in previous work on these databases (Boyle et al, 2013). Figure II.9.3.1 shows possible patient trajectories; incident users (with no history of anti-diabetic treatment) are patients 5, 6 and 7 on this diagram. As all prescription databases were set up relatively recently (i.e. 2004-2005), and we will have many patients in the cohort that developed diabetes long before that, the new user approach will deal with patients for whom we have complete data on the history of anti-diabetic medication.

The period of follow-up begins at that time or three months later until a specified event takes place, either (1) date of cancer/or acute pancreatitis diagnosis; (2) date of death (right censoring, only if death occurred before the last date of available data in registry); and, (3) last date of available data in cancer registry.

Figure II.9.3.1: possible patient trajectories

Acute pancreatitis cases will be identified from the hospital discharge registers. The diagnosis of acute pancreatitis is a clinical diagnosis that hinges on the presence of abdominal pain and elevation of two biomarkers, themselves not diagnostic. One potential issue to be faced is that abdominal pain can be an unwanted side effect of the use of GLP-1 medication and this could lead to diagnostic bias.

Cases of all thyroid cancers (especially medullary thyroid cancer) and pancreatic cancer will be identified from the national cancer registers. However, data on the cancer cases for a given year are typically considered incomplete until approximately one year after the year ends. Therefore, it will be possible to use the national cancer registries in these three countries to identify incident cancers occurring until the end of 2012, if the analysis of thyroid cancer is planned to be performed in early 2014.

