A potentially major issue surrounds the well-documented under-diagnosis of pancreatic cancer in some Cancer Registries. Kilander et al (2012) recently examined this situation in the Swedish Cancer Registry. From a total of 31,067 cases of pancreatic cancer, 44% were registered in the Hospital Patient Discharge Register but not in the Cancer Registry indicating an overwhelming under-reporting of pancreatic cancer in the Cancer Registry. Thus, diagnoses of pancreatic cancer will be sought in both the Cancer Registry and the Hospital Patient Discharge Registry in each of the countries.

Covariates

The key variables in the study will be obtained from the prescription databases (age, gender, insulin and other diabetes medications and other prescriptions); the hospital discharge registries (date of diagnosis, gallstones and obstruction of the pancreatic duct); the cancer registries (date of diagnosis, cancer site, histology and outcome of cancer); and the national death registers (date and cause of death).

All analyses will be stratified by age and gender and in addition by treatment history.

In order to improve the analysis all efforts will be made to collect additional information on several other potential confounding variables.

Potential confounders for pancreas cancer will include smoking history, alcohol intake, family history of pancreas cancer, a previous diagnosis of Multiple Endocrine Neoplasia (especially MEN1) and chronic pancreatitis.

Potential confounders for acute pancreatitis will include duration of diabetes, presence of gallstones, prior use of anti-diabetic medications, alcohol intake and obstruction of the pancreatic duct.

Potential confounders for thyroid cancer will include duration of diabetes, prior use of anti-diabetics, radiation treatment to the head and neck, iodine intake, hormonal and reproductive treatment, history of goiter or benign thyroid nodules, history of cancer, diagnosis of Multiple Endocrine Neoplasia type 2 (MEN2), and family history of medullary thyroid cancer at the baseline.

The availability of these additional data will differ between the individual countries. A dictionary of compatible covariate information will be compiled at the outset of the study to enable information common to more than one study to be collected and recorded in a manner that will enable the data to be used across studies.

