The Swedish cohort will comprise patients included in the Prescribed Drug Register, who have been prescribed GLP-1 agonists or other anti-diabetic drugs. By linkage to the regional cancer registries in Sweden as well as hospital discharge registries, information on cancer incidence and pancreatitis will be obtained.

Sweden has a highly efficient National Population and Death Register where record linkage has been done effectively on such studies. This gives coverage of all deaths in Sweden and the ability for record linkage ensures that all members of the cohort who die can be identified. In addition, Sweden has a number of other national registers that may be used to add information on potentially confounding factors.

Overall

The personal identification number will be used to link unambigously the databases in each country. The ATC coding system (Anatomic Therapeutic Coding) will be used to identify exposure: all patients having been prescribed drugs for the treatment of diabetes (ATC code A10 and subcategories) will be retrieved and linked to the other databases: they will be followed via cancer and hospital discharge registries. The ICD10 codes will be used for outcome assessment: acute pancreatitis (K85), pancreatic cancer (C25) and thyroid cancer (C73), especially medullary thyroid cancer (Thyroid cancer is a distinct entity in the ICD10 and the tumour type can be determined by the ICD-0 code).

II.9.5 Study size (Sample size and study power)

A key consideration in designing studies is the requirement for a large enough number of events (pancreatitis, pancreatic cancer and thyroid cancer) to provide adequate statistical power to detect an effect. A conservative approach to estimating statistical power has been adopted, since the cumulative rate of events will be greatly increased as longer follow-up time is available.

Assuming an average prevalence of T2DM of 5% (Carstensen et al, 2008) for a total adult population (20+ years) in the 3 countries (Denmark, Norway and Sweden) of 15,000,000, our study population will reach approximately 750,000 subjects.

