Patients who develop pancreatic cancer and thyroid cancer will be identified as well anyone who is diagnosed with pancreatitis, and their complete clinical information will be retrieved and collected from existing national registers and databases annually: smoking history, a previous diagnosis of Multiple Endocrine Neoplasia (especially MEN1), chronic pancreatitis, duration of diabetes, gallstones, prior use of other anti-diabetics, alcohol intake, obstruction of the pancreatic duct, radiation treatment to the head and neck, iodine intake, hormonal and reproductive treatment, diagnosis of Multiple Endocrine Neoplasia type 2 (MEN2), history of goitre or benign thyroid nodules, history of cancer, and family history of medullary thyroid cancer.

Outcomes of interest

Acute pancreatitis cases will be identified from the hospital discharge registers. Cases of thyroid cancer and pancreatic cancer will be identified from the national cancer registers. However, data on the cancer cases for a given year are typically considered incomplete until approximately one year after the year ends. For example, it will be possible to use the national cancer registries to identify incident cancers occurring until the end of 2013, if the analysis of thyroid cancer is planned to be performed in early 2015.

Exposure assessment and follow-up time

Patients with one or more prescriptions of lixisenatide will be identified from the national prescription registers and included in the register.

For acute pancreatitis, the exposure duration on lixisenatide will begin accumulating on the first day of lixisenatide prescription and continue with the subsequent continuous use of lixisenatide until:

- 1) the end of the lixisenatide treatment (in addition to a grace period of up to 30 days, to account for non-adherence),
- 2) the occurrence of acute pancreatitis, or;
- 3) the end of registry, whichever comes first.

For thyroid cancer and pancreatic cancer, the exposure duration will start from the first day of lixisenatide prescription and continue until either (1) the occurrence of thyroid cancer or pancreatic cancer, or (2) the end of registry, whichever comes first.

III.9.4 Data Sources

Patient registry data sources are the same as for the data base study (Section II.9.4)

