Adequate training of the staff will be essential in order to correctly recognize and report all events of interest. Systematic collection of follow-up data, routine follow-up of all registry patients for the key adverse effects previously identified, as well as all other information.

In each centre data will be linked between the different data sources (population registry, prescription registry, hospital discharge registry, cancer registry) through an anonymized unique identification number. Linking the population registry, the prescription registry and the cancer registry has already been tested and proved to be effective through our previous database study (Boyle et al, 2013). However, linking with the hospital discharge registry requires a procedure preventing introduction of information bias in the study.

All patients identified to have had an anti-diabetic treatment in the prescription database (regardless of the type of medication taken) will be linked to the Hospital Discharge Registry. All discharge information will be retrieved for all the diabetic patients (with an anti-diabetic prescription) and searched for codes or keywords that indicate a pancreas related disease. For the purpose of this task, in each country a Medical Adjudication Committee (MAC) will be assembled, composed of at least two internists, who will be blinded as to treatments taken by patients. The MAC will examine all charts of potential pancreatitis patients receiving lixisenatide and also patients receiving other GLP-1 receptor agonists. They will be responsible for:

- Establishing a disease definition for acute pancreatitis²;
- Identify codes or keywords in hospital discharge records possibly associated with pancreatitis;
- Contact hospitals (through a standardized questionnaire) for getting full information on the data the diagnosis of pancreatitis was based on
- Review data for establishing whether pancreatitis was present.

After that the MAC assessment will be entered in the study database, the analyses in function of the treatment type (lixisenatide, other GLP-1 RAs or other anti-diabetic drugs) will be made following a review by the MAC of some patients not thought to have pancreatitis (to confirm the absence of the disease).

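### The Registry's observed/expected test takes its expected counts from Database Study rates, but the case definitions for pancreatic cancer and acute pancreatitis are not aligned between the two studies

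*Protocol*

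**What the plan says.** **The test.** Under III.9.7, for all three outcomes, "the expected number of cases will be estimated annually after launch using the background rates obtained from the retrospective databases study". If the observed count "is significantly higher than the expected number of cases, further investigation may be warranted". The Part III synopsis gives the same rule.

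**Pancreatic cancer.** II.9.3 first names the national cancer registers as the source. It then reports that, of 31,067 Swedish cases, 44% were in the discharge register but not in the cancer registry, and concludes: "Thus, diagnoses of pancreatic cancer will be sought in both the Cancer Registry and the Hospital Patient Discharge Registry in each of the countries". For the Registry, III.9.3 says "Cases of thyroid cancer and pancreatic cancer will be identified from the national cancer registers" and adds no such correction. However, III.9.4 and the Part III synopsis link both the cancer registries and the discharge schemes for identifying cancer cases, and III.9.4 says the data sources are the same as in the Database Study.

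**Acute pancreatitis.** II.9.3 and III.9.3 share one sentence: "Acute pancreatitis cases will be identified from the hospital discharge registers". II.9.4 and III.9.4 also share the coding sentence: "The ICD10 codes will be used for outcome assessment: acute pancreatitis (K85), pancreatic cancer (C25) and thyroid cancer (C73"). Part II contains no adjudication step. In Part III, a Medical Adjudication Committee (MAC) in each country sets the disease definition, obtains hospital data and decides whether pancreatitis was present. On whose charts are reviewed, III.9.6 says: "The MAC will examine all charts of potential pancreatitis patients receiving lixisenatide and also patients receiving other GLP-1 receptor agonists".

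**The concern.** An observed/expected ratio estimates relative risk only if a case means the same thing above and below the line. Suppose the Registry captures a fraction k of the cases that the Database Study definition would have counted in the same patients. The ratio then estimates the true relative risk multiplied by k. With k below 1, a true excess is shrunk and can disappear. With k above 1, the Registry raises false alarms. The Registry exists to detect an excess quickly and reliably (III.8), and III.9.7 rests the decision on this comparison.

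**Working it through.** **Inputs.** III.9.5 gives 1,049,810 prevalent diabetes cases (493,210 in Sweden), 55,000 new cases a year, and rates of 65.57 (pancreatitis) and 29.19 (pancreatic cancer) per 100,000 person-years. II.9.3 gives the Swedish 44%. The share of pancreatitis cases that the MAC will confirm is not in the document, so a range is assumed.

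**The plan's own figures at 1% exposure.** Person-years = 5 × 0.01 × 1,049,810 + 10 × 0.01 × 55,000 = 57,990.5. Expected cases are 57,990.5 × 65.57/100,000 = 38.02 and 57,990.5 × 29.19/100,000 = 16.93. Both agree with the tables. The plan does not state sidedness; an exact one-sided 5% Poisson test is used here. It gives 0.87 for pancreatitis at a ratio of 1.5 (plan: 0.83) and 0.95 for pancreatic cancer at a ratio of 2 (plan: 0.92). The plan's values appear at neighbouring expected counts (0.833 at E = 35; 0.919 at E = 15), which fits table look-up. They are not disputed.

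**Formula.** The critical count c is the smallest c with P(X ≥ c | E) ≤ 0.05. Power = P(X ≥ c | ratio × k × E).

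**Pancreatic cancer, if III.9.3 governs.** If only Sweden under-registers, k = 1 − 0.44 × 493,210/1,049,810 = 0.79. If the Swedish figure held in all three countries, k = 0.56. With E = 16.93, c = 25:

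| k | Ratio shown when the truth is 2 | Power at 2 | Power at 1.5 |
|---|---|---|---|
| 1 | 2.00 | 0.95 | 0.56 |
| 0.79 | 1.59 | 0.67 | 0.16 |
| 0.56 | 1.12 | 0.10 | 0.006 |

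The planning rate comes from NORDCAN (II.9.5), not from the two-source rule, so the two-source expected count may be higher. Scaled for Sweden only, E = 16.93/0.793 = 21.3 and c = 30; power at a true ratio of 2 is then 0.77, against 0.98 with matching definitions. Scaled for all three countries, E = 16.93/0.56 = 30.2 and c = 41; power is 0.13, against 0.997. The ratio stays at or below 1 until the true relative risk passes 1/k, which is 1.26 or 1.79. If III.9.4 governs instead, k = 1 and this bias does not arise.

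**Acute pancreatitis.** With E = 38.02, c = 49 and a true ratio of 1.5:

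| Net capture relative to K85 (assumed) | Ratio shown | Power |
|---|---|---|
| 100% | 1.50 | 0.87 |
| 95% | 1.42 | 0.78 |
| 90% | 1.35 | 0.65 |
| 80% | 1.20 | 0.33 |

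In the other direction, net capture of 110% raises the false-alarm rate under no effect from 0.049 to 0.15.

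**Which hypotheses (III.8).** Hypotheses 1 and 4 concern pancreatitis. Users of other anti-diabetics are not named for chart review, so hypothesis 4 is not like-for-like. Other GLP-1 RA users are named, but hypothesis 1 is not like-for-like either while its expected counts come from the Database Study. Hypotheses 2 and 5 (pancreatic cancer) depend on the cancer source. Hypotheses 3 and 6 (thyroid cancer) are unaffected: both studies use the cancer registers and the MAC has no role.

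**The case against.** The strongest reply is that the text is ambiguous rather than wrong. K85 and C25 are repeated for the Registry, III.9.4 links discharge records to find cancer, and III.9.7 never says that the observed pancreatitis count is restricted to MAC-confirmed cases. That stands in part. MAC confirmation is an inference from III.9.6, where the committee's assessment is entered before the treatment analyses, and from its listed task of verifying the diagnosis. The pancreatic cancer point is a conflict inside Part III, not a settled narrower definition. But the passages still have to be reconciled, because the decision rule depends on which one applies.

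A reader might infer that the ratio is certainly biased downward. The documents do not support that. For pancreatic cancer it depends on III.9.3 governing. For pancreatitis, adjudication should remove false positives, and II.9.1 expects over-coding in GLP-1 RA users. But the MAC sets its own definition, works from codes and keywords and reviews some presumed negatives, so net capture could exceed K85. A reader might also infer that a doubling of pancreatic cancer would generally be hidden. That needs the Swedish 44% in Denmark and Norway, whose cancer registries II.9.4 describes as complete.

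The protocol concedes possible differences in diagnostic accuracy between periods (III.8) and foresees methodological comparison of the two studies (III.9.9). Neither aligns the case definitions.

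**Conclusion.** The point holds in conditional form: the observed/expected test is not secured as like-for-like, and the relevant sections conflict.

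- **Pancreatic cancer:** if III.9.3 governs, the bias is downward. At 1% exposure, power for a true ratio of 2 falls from 0.95 to about 0.67 under Sweden-only under-registration (0.77 if the expected count is scaled up). It falls to about 0.10 only if 44% is assumed everywhere.
- **Acute pancreatitis:** the bias is probably downward, with power for a ratio of 1.5 falling from 0.87 to between 0.78 and 0.33 over an assumed 95% to 80% confirmation. An upward bias cannot be excluded. Hypotheses 1 and 4 are affected. It would be wrong to extend the adjudication problem to hypotheses 5 and 6, which concern cancers that the MAC does not review.

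These figures assume an exact one-sided 5% Poisson test and the plan's own person-years and rates.

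**What to change.** 1. In III.9.3, identify Registry pancreatic cancer from the cancer registry plus hospital discharge records, as in II.9.3, and make III.9.3 and III.9.4 agree.
2. In III.9.7, state that each observed/expected comparison uses the same case definition in numerator and denominator. For acute pancreatitis, report K85 discharges against K85 rates wherever the expected count comes from the Database Study. Compare MAC-confirmed cases only with MAC-confirmed comparators, that is, the other GLP-1 RA users whose charts are reviewed.

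The cost is mainly protocol wording: the sources are already linked and K85 is already the outcome code in both studies. The downside is that K85 against K85 keeps the over-coding in GLP-1 RA users that II.9.1 expects, which matters most against other anti-diabetics. The two pancreatitis results should therefore be read together. Adjudicating a sample of Database Study cases is an alternative, but it needs additional chart review.
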